5.3 Design and Procedure

A maximum of 36 patients with a newly diagnosed, previously untreated WHO grade 4 malignant glioma that is IDH wildtype, MGMT promoter unmethylated will be treated in this study after undergoing standard of care surgical resection followed by 3-6 weeks of radiation therapy (XRT) with or without concomitant TMZ and providing informed consent. Patients will consent to this study after completion of XRT/TMZ, as long as they will be able to start treatment within 8 weeks of the end of XRT/TMZ (and as long as this is felt to be in the best interest of the patient by the treating physician). Patients will receive seven P30-EPS peptide vaccines over two phases. The first 5 vaccines will be given during the Priming Phase (day 1 through day 22). The final 2 vaccines will be given during the Booster Phase (day 84 [\pm 7 days] and day 140 [\pm 7 days]). During the Booster Phase from Day 84 onwards, patients will also be given 20 μ g/kg Hiltonol[®] injections to be administered at home every 2 weeks until they return to the clinic on Day 140. Blood will be drawn throughout the study to investigate the immune response to P30-EPS vaccination. We will also request archival tumor tissue from patients' baseline surgical resection or prior biopsy, as well as tumor tissue from future surgeries, but only in the case that the patients may undergo other clinically indicated biopsy or tumor resection while participating in this study. Available tumor tissue will be analyzed by correlative analyses as outlined in Section 9.3.

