MEK-ERK activating mutations will be queried using existing WES data. qIHC will be performed for p-ERK1/2 and TMEM119 as described by Arrieta et al *Nature Cancer* 2021 [71].

To define T cell exhaustion/inhibitory receptors, we will also similarly quantify and define spatial PD-L1, CTLA4, PD1, TIGIT, and TIM3 expression in all tumor samples, using qIHC. Bulk RNA-seq data will be used to determine MHC-class II, IFN γ and cell cycle gene expression signatures, as well as differential expression of inhibitory receptors (TIGIT, TIM3, CTLA4, and PD1).

Neoantigen depletion will be predicted using the pVAC-seq pipeline. Briefly, for the pVAC-seq pipeline, neoantigens will be defined at 8-11-mer peptides from exonic nonsynonymous single nucleotide variants that bind to a patient's respective HLA class I molecule with a binding affinity score <500nM stronger than the wildtype peptide using NetMHCpan51. Neoantigen density will be expressed as ratio of observed to expected neoantigens. Expected neoantigen levels will be determined using a previously empirically derived rate of mutation that assumes no selection against neoantigen-causing mutations normalized to the silent mutation load for each patient's tumor [75]. MHC class I epitope predictors are imperfect in predicting actual MHC class I binding epitopes [76]. Thus, nonsynonymous mutation/TMB ratios will also be used to predict neoantigen depletion: lower non-synonymous mutations out of total mutations is surrogate measure of neoantigen density [77].

Each feature will be tested for its association with post- P30-EPS vaccine survival to determine if other biomarkers are superior in identifying P30-EPS vaccine responsive GBM patients. We will also test the relationships between each biomarker to determine if they identify the same patients, and to further define the nature of patients living longer after P30-EPS vaccination.

The associations between the various biomarkers will be explored with scattergrams, and correlation (Pearson or Spearman) with adjustment for multiple comparisons. For each biomarker, Receiver-operating curves will be performed to

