assess the optimal threshold for differentiating short versus long-term survival; the sensitivity and specificity of each biomarker will be compared. A Cox proportional hazards model will assess the joint effect of all biomarkers on survival to discern if an integrated biomarker approach is more effective in predicting survival outcome. Correction for multiple comparisons using gene expression analyses will use the False Discovery Rate.

15.7.3 Exploratory Objective: Assess resected tumor for expression of the vaccine targets (i.e. EphA2, pp65, and survivin)

Objective: Assess resected tumor for expression of the vaccine targets (i.e. EphA2, pp65, and survivin)

Analysis Set: Any available tumor tissue from patients on-study prior to and/or after P30-EPS vaccination

Outcome: Association between the vaccine targets (EphA2, pp65, and survivin) and clinical outcomes

Hypothesis: Expression of vaccine targets will associate with survival and other exploratory endpoints

Analysis Plan: RNA-seq analysis of tumor tissue will be used to determine expression levels of vaccine targets, in transcripts per million and expression will be linked with survival and PFS after P30-EPS vaccination. For patients with available post-P30-EPS vaccination tumor tissue, pre- vs post P30-EPS vaccine expression levels of antigens will be determined to test if antigen escape/immunoediting of vaccine antigens occurs as well as if T cell inflammation post- P30-EPS vaccination associates with vaccine antigen expression.

15.7.4 Exploratory Objective: Assess changes in the tumor immune microenvironment, mutational heterogeneity/clonality, neoantigen depletion, and their association with survival.

Objective: Assess changes in the tumor immune microenvironment, mutational heterogeneity/clonality, neoantigen depletion, and their association with survival.

Analysis Set: Any available tumor tissue from patients on-study prior to and/or after P30-EPS vaccination

Outcome: Since productive immune surveillance is associated with immunoediting (e.g., depletion of immunogenic glioma cell clones), the associations between putative neoantigen depletion, mutational heterogeneity, gene expression signatures of T cell inflammation, and survival will be tested.

Hypothesis: Neoantigen depletion, reduced mutational heterogeneity, and increased T cell inflammation will be associated with improved survival in GBM patients treated with the P30-EPS vaccine.

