These analyses are exploratory and will primarily leverage qualitative comparisons. Changes in TMB, neoantigen levels, cellular phenotypes, and mutation clonality will be qualitatively compared within patients and tested using paired t-tests. Comparisons of TMB/neoantigen depletion, gene expression, and clonality to TMB and post-P30-EPS vaccine survival will be performed using Spearman correlation, adjusted for multiple comparisons. Similarly, the change in each of these features will be correlated. SnRNAseq (tumor immune microenvironment) based analyses are largely intended to be qualitative assessments that will be tested for correlation with TMB and post- P30-EPS vaccine survival. Differential expression analysis

(DEseq2) for snRNAseq data will be adjusted for multiple comparisons using the False Discovery Rate.

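### Section 15.7.3 reads antigen escape from whole-tissue RNA-seq without accounting for tumour content, so a change in tumour fraction can mimic or hide escape, and each pre/post pair also spans chemoradiation

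*Combined protocol and SAP*

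**What the plan says.** Section 15.7.3 states the assay and scale: "RNA-seq analysis of tumor tissue will be used to determine expression levels of vaccine targets, in transcripts per million". Where post-vaccine tissue exists, "pre- vs post P30-EPS vaccine expression levels of antigens will be determined to test if antigen escape/immunoediting of vaccine antigens occurs". The same sentence adds a second question, "if T cell inflammation post- P30-EPS vaccination associates with vaccine antigen expression".

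The section gives no tumour-fraction estimate, minimum tumour content, deconvolution or tumour-cell-restricted readout. It also names no test, significance level or decision rule for the pre/post comparison.

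Other relevant text:

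- **Tissue source.** Section 5.3 takes tissue from the "baseline surgical resection or prior biopsy, as well as tumor tissue from future surgeries", the latter only when surgery is clinically indicated. Patients enter after "undergoing standard of care surgical resection followed by 3-6 weeks of radiation therapy (XRT) with or without concomitant TMZ".
- **Type of RNA-seq.** Section 15.7.3 does not call its RNA-seq bulk. Section 15.7.2 does so for the tissue signatures: "Bulk RNA-seq data will be used to determine MHC-class II" and other signatures.
- **Within-patient test.** Section 15.7.4 says changes in mutational burden, neoantigens, cell phenotypes and clonality will be "qualitatively compared within patients and tested using paired t-tests". Vaccine-antigen expression is not on that list.
- **Cell-level and DNA data.** Section 15.7.4 offers single-nucleus RNA-seq as an option in a subset, for qualitative use. It plans exome-based copy-number calling and clonal deconvolution, with cancer cell fractions, for patients with paired tissue. Neither is tied to the 15.7.3 comparison.
- **Expression outside tumour.** Section 7.2.1 treats CMV antigens as absent from normal brain.

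**The concern.** Whole-sample expression mixes two quantities: how much target each tumour cell expresses, and what share of the sample is tumour. Only the first bears on escape. A later specimen with more necrosis, reactive tissue or immune cells can show lower antigen TPM although no tumour cell has lost antigen. A later specimen richer in tumour can mask a real loss.

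The inflammation question has the same weakness. More immune cells raise a T-cell signature and dilute tumour transcripts, so a negative relation can arise without immunoediting.

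Apart from composition, a pair built on the baseline surgery spans chemoradiation as well as vaccine. Any true per-cell change could come from either.

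At stake is a false lead about escape, or a missed one, in an analysis meant to generate hypotheses. Such a lead could influence antigen choice in a later trial.

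**Working it through.** The plan gives no figure for this comparison, so there is nothing of its own to reproduce. The check asks how far tumour content alone can move the result.

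**Inputs from the documents.** RNA-seq TPM on tumour tissue (15.7.3); baseline tissue before, and post-vaccine tissue after, radiation with or without temozolomide (5.3); at most 36 patients (15.9).

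**Assumptions, not in the documents.** Tumour fraction falls from p0 = 0.8 to p1 = 0.6. Expression per tumour cell, T, is constant (no escape). Non-tumour cells express the target at a fraction f of the tumour level. Tumour and non-tumour cells contribute RNA equally. The paired log2 change has SD 0.5 to 0.8. A two-sided 5% paired t-test is used with 5 or 10 pairs.

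**Formulas.** Sample expression is E = T[p + (1 − p)f]. With no escape, the expected log2 change is

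δ = log2{[p1 + (1 − p1)f] / [p0 + (1 − p0)f]}.

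The rejection rate comes from the noncentral t distribution with n − 1 degrees of freedom and noncentrality δ√n / SD.

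**Shift.**

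- f = 0: log2(0.60/0.80) = −0.415
- f = 0.25: log2(0.70/0.85) = −0.280
- f = 0.5: log2(0.80/0.90) = −0.170
- f = 1: 0

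Example for f = 0, n = 10, SD 0.5: noncentrality is 0.415 × 3.162 / 0.5 = 2.62 in absolute value, which gives 65% rejection.

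**False-positive rate (SD 0.8 to SD 0.5; nominal 5%).**

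| f | 5 pairs | 10 pairs |
|---|---|---|
| 0 | 15-30% | 31-65% |
| 0.25 | 9-16% | 17-35% |
| 0.5 | 7-9% | 9-16% |
| 1 | 5% | 5% |

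For a smaller fall, 0.8 to 0.7 with f = 0, the rates are 7-10% with 5 pairs and 10-19% with 10.

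**A second set of assumptions.** A separate simulation used 20,000 runs, a starting fraction of 0.70, between-sample SD of tumour fraction 0.10, and residual SD 0.5 log2 per sample. With f = 0 and 4, 6 or 10 pairs, a fall to 0.60 gave 7, 9 and 13%; a fall to 0.50 gave 15, 23 and 43%. With no fall, the rate was about 5%.

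**The opposite direction.** If tumour fraction rises from 0.50 to 0.70 with f = 0, the shift is log2(0.70/0.50) = +0.49. A true per-cell loss of 1 − 0.50/0.70 = 29% would then leave the sample-level value unchanged.

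**Inflammation against antigen.** The model takes log antigen = log(p) + noise and log T-cell signature = log(1 − p) + noise, with p between 0.3 and 0.9 and no true link. Spearman's test rejects in 8-42% of runs at n = 10 and 11-80% at n = 20 (noise SD 0.8 to 0.3). With p only between 0.5 and 0.8, it rejects in 6-20%.

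**Effect of adjustment.** The paired test returns to about 5%, even with error in the estimated tumour fraction. The Spearman test does so only if tumour fraction is known without error. At n = 20 and noise SD 0.3, estimation error of SD 0.10 leaves about 17-22% false positives, and SD 0.15 leaves about 31-38%, depending on how the adjustment is made.

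**The case against.** The strongest reply is that no formal test is at risk. Section 15.7.3 states an outcome and hypothesis about association with clinical results; the escape comparison is one clause, with no null hypothesis or decision rule. A reader might infer that the trial will run a 5% test that rejects whenever tumour content falls. The documents do not support that: the paired t-test belongs to 15.7.4 and to a list that omits vaccine antigens. The rates above describe an assumed test.

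The size is also fragile. Zero expression outside tumour has support only for CMV pp65. Section 7.2.2 calls survivin overexpressed in cancers, not exclusive to them. Ten pairs would be 28% of the maximum 36 patients, and post-vaccine tissue depends on clinically indicated surgery. The documents do not say which way tumour fraction would move. Applying the largest rates to EphA2 or survivin would go too far.

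Finally, Section 9.3 already calls the tissue work hypothesis generating and without statistical power. Optional single-nucleus data may help in some patients, and tissue handling is partly deferred to a laboratory manual that is not among the documents, so a tumour-content rule may exist there.

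These points limit size and severity but do not remove the concern. Low power is a caveat about precision; this is a bias, and more pairs would make a spurious shift easier to declare. The single-nucleus work is neither assured nor linked to the comparison.

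**Conclusion.** The concern holds in a limited form. As written, the 15.7.3 comparison cannot tell loss of antigen by tumour cells from a change in tumour content, and it can err in either direction. It matters most for pp65, on the protocol's own premise about normal brain, and less for targets that non-tumour cells also express. That the measure is whole-tissue is an inference from TPM on tumour tissue and from 15.7.2, but a well-supported one.

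The false-positive rates in the working rest wholly on assumed values. They range from nominal, when non-tumour cells express the target equally, to well above it, when they do not express it and the fall in tumour fraction is substantial.

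Two further inferences should be resisted. Adjustment for tumour fraction does not cure everything: error in the estimate leaves confounding in the inflammation association. Nor would a contrast with non-targeted genes isolate the vaccine effect, because chemoradiation can alter a target gene differently from the comparison genes.

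The analysis is exploratory. No primary or secondary endpoint, dose decision or sample size depends on it.

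**What to change.** Amend 15.7.3 as follows:

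1. Name the paired method. Report log-expression changes for each target both unadjusted and adjusted for tumour fraction, estimated from the exome copy-number and clonality pipeline in 15.7.4.
2. Give the inflammation-antigen association with the same adjustment, and note that error in the tumour-fraction estimate leaves residual confounding.
3. Call a change consistent with escape only if it persists after adjustment.
4. State that a pre/post change cannot be attributed to vaccine rather than to radiation with or without temozolomide unless paired tissue from unvaccinated patients is available.
5. If a contrast with non-targeted genes is shown, label it supportive only.

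The cost is wording and some extra analysis of data already planned; no new samples are needed. The downsides are added noise from the tumour-fraction estimates, possible over-correction for targets that non-tumour cells express (hence reporting both versions), and loss of pairs without exome data.

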15.6.5 Secondary Objective: Survival and PFS

Objective: Describe the survival and PFS of patients who received a P30-EPS vaccine

Analysis Set: All patients who initiate P30-EPS vaccine treatment

Outcome: Survival time is the time between first P30-EPS vaccination and death, or last patient follow-up if the patient remains alive. PFS is defined as the time between first P30-EPS vaccination and initial failure (disease progression or death). PFS is censored at the last follow-up, if the patient remains alive without disease progression.

Hypothesis: Descriptive

Analysis Plan: The Kaplan-Meier estimator will describe the survival of patients treated on this protocol. Median survival will be estimated with confidence intervals, along with estimates for 12, 24, and 36-month survival.

Additionally, the Cox proportional hazards model may explore the impact of CMV status on survival and PFS outcome.

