Analysis Plan: The following assessments will be made if samples are available from patients who have baseline tumor tissue and tissue from a second surgical procedure after they have received the P30-EPS vaccine.

1. TMB suppression and putative neoantigen: will be determined to test if low TMB status in GBM is associated with TMB suppression and/or neoantigen depletion, or post-P30-EPS vaccination survival.
2. Gene expression signatures: T cell inflammatory/MHC class II gene expression signatures, and unbiased gene set enrichment analyses (Biocarta and Reactome), and long (overall survival >24 months) vs short (overall survival <24 months) survival will be performed to determine if patients with low TMB and/or longer survival after P30-EPS vaccine exhibit distinct gene expression signatures and/or changes in specific gene expression patterns in response to P30-EPS vaccine.
3. Mutational heterogeneity/clonality: will be predicted using subclonal deconvolution of WES for all samples using a pre-validated pipeline employing Mutect2 [78] for SNV and InDel calling, FACETS [79] for CNV calling, and PyClone-VI [80] for sub-clonal deconvolution. Cancer Cell Fractions (CCF) for each mutation within each sample will be determined and sample-mean CCFs will be tested for their relationship with post- P30-EPS vaccine survival and TMB.

To more comprehensively define the relationships between TMB and post- P30-EPS vaccine survival with the GBM tumor immune microenvironment and mutational clonality, single nuclei RNA sequencing (snRNAseq) may be performed for a subset of tumor samples. In addition, tumors from any patients surviving >24 months post-P30-EPS vaccine will also be analyzed, in order to ensure an informative comparison of post- P30-EPS vaccine survival with these features.

snRNAseq will be performed on snap frozen tissue to qualitatively define the tumor microenvironment and link tumor microenvironment features with vaccine antigen expression, mutational landscapes, and survival. snRNAseq will also be used to define exhaustion and immunosuppressive phenotypes of tumor-associated macrophages in post- P30-EPS vaccine tissue, as well as whether these cell type densities or states differ according to TMB or long vs. short survival.

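### Exploratory marker analyses relate a censored survival time to tumour features by methods that cannot use censored times; second-surgery features and PFS need a stated clock and censoring date (minor)

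*Combined protocol and SAP*

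**What the plan says.** **Endpoint definitions (15.6.5).** "Survival time is the time between first P30-EPS vaccination and death, or last patient follow-up if the patient remains alive". For PFS: "PFS is censored at the last follow-up, if the patient remains alive without disease progression". Both clocks start at the first vaccination. Survival is summarised by Kaplan-Meier, with estimates at 12, 24 and 36 months, so the plan expects some patients to be censored.

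**Marker analyses.** Section 15.7.2 says "For each biomarker, Receiver-operating curves will be performed to" and goes on: "assess the optimal threshold for differentiating short versus long-term survival". It gives no month cut-point. It also plans a Cox model, but only for the joint effect of all biomarkers. Section 15.7.4 uses rank correlation: "Comparisons of TMB/neoantigen depletion, gene expression, and clonality to TMB and post-P30-EPS vaccine survival will be performed using Spearman correlation". For gene-expression signatures it contrasts "long (overall survival >24 months) vs short (overall survival <24 months) survival". Its assessments are to be made in "patients who have baseline tumor tissue and tissue from a second surgical procedure after they have received the P30-EPS vaccine".

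**Disease assessment.** Section 9.1 and Table 3 schedule on-treatment MRI before vaccines #5, #6 and #7 (Days 22, 84 and 140) and none later. Section 12.5.2 follows every vaccinated patient for PFS and survival until death or loss to follow-up.

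**The concern.** There are three separate issues.

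1. **Censoring.** A Spearman coefficient, an ordinary ROC curve and a two-group split each need a known survival time, or at least a known class, for every patient. A patient alive at 15 months has neither. The analyst must rank that patient as if death occurred at 15 months, drop the patient, or guess the class. The plan does not say which.
2. **Time origin.** A patient contributes second-surgery tissue only by living to that surgery. If survival is counted from vaccine #1, the interval to surgery is part of the outcome. A feature that drifts with that interval then shares a component with survival.
3. **PFS censoring date.** Contact without a disease assessment can be counted as progression-free time.

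Section 9.3 describes the biomarker findings as hypothesis-generating. At stake is whether a marker carried forward reflects biology or merely follow-up length and surgery timing, and whether the PFS curve reflects assessed time.

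**Working it through.** The documents give no power, alpha or event count for these analyses, so there is no figure to reproduce. The text settles whether the methods fit the endpoint. Simulation only illustrates size.

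**A. Effect of censoring on Spearman and on a 24-month split**

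From the documents: maximum n = 36 (15.9), the 24-month split (15.7.4), and median survival of 16.1–20.5 months for newly diagnosed GBM (5.2), used to set the range. Assumed: exponential survival with median 12, 16 or 20 months from vaccine #1, hazard ratio 0.6 per SD of the marker, uniform censoring, two-sided alpha 0.05, 4,000 replicates.

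Observed time is Y = min(T, C). The check compares Spearman(marker, T) with Spearman(marker, Y), and counts the true survivors beyond 24 months (T > 24) who have Y < 24.

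| Follow-up (months) | Censored | Rho, true times | Rho, observed times | Power, true → observed | True >24-month survivors with Y < 24 |
|---|---|---|---|---|---|
| 12–36 or 6–48 | 28–44% | about 0.38 | 0.27–0.34 | about 0.65 → 0.39–0.55 | 43–50% |
| 24–60 | 14–27% | about 0.38 | 0.35–0.37 | about 0.65 → 0.58–0.63 | none |
| 120 or more | 1–4% | about 0.38 | about 0.38 | no loss | none |

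The loss is material when many patients are censored early, small once everyone has 24 months, and absent when follow-up is nearly complete.

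**B. Survival timed from vaccine #1 in patients selected for a second surgery**

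Assumed: 6, 10 or 12 patients with a second surgery, exponential survival T with median 12 or 16 months, exponential time to surgery S with median 9 months, no censoring, 6,000 replicates. Patients enter only if S < T. The feature change is slope × S/9 + N(0,1), with no effect on remaining survival.

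- Slope 0.5 or 1, clock from vaccine #1: mean rho 0.13–0.24, type I error 0.06–0.13.
- Same data-generating model, clock from second surgery: mean rho about 0 (−0.01 to 0.01), type I error 0.05–0.06.
- Slope 0, clock from vaccine #1: mean rho about 0, type I error 0.05–0.06.

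The spurious correlation therefore needs a feature that depends on time to surgery. Selection appears either way: with a median of 12 (16) months overall, patients reaching surgery have a median of about 21 (26) months. The hazard here is constant, so restarting the clock removes the artefact exactly. If the hazard varies with time since vaccination, delayed entry is the safer form.

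**C. PFS**

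Day 140 is 139 days after Day 1, or 139/30.4 = about 4.6 months. Take the extreme case of a patient never assessed again and last contacted, apparently progression-free, at 12 months. The stated rule credits 12 − 4.6 = 7.4 months without an assessment. Staying longer in the risk set without an event can leave the Kaplan-Meier curve unchanged or raise it, but cannot lower it. How many patients this affects cannot be derived from the documents.

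**The case against.** The best defence is follow-up. Section 12.5.2 follows patients to death or loss, Sections 9.4 and 12.4 end the study only after follow-up is complete, Section 15.6.5 plans 36-month estimates, and Section 15.8 rules out interim efficacy analyses. In a disease that Section 7.1 calls universally fatal, a late analysis could have little censoring, and the Spearman and ROC objection would then almost vanish. This stands as a limit on size. It does not remove the gap: I find no data cut-off or minimum follow-up for the marker analyses, and entry is staggered. Section 10.1.4 reports the first six patients treated as of April 2024 and a second six still under DLT observation, out of at most 36.

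The plan is also modest about these analyses. Section 9.3 disclaims power, and Section 15.7.4 says its comparisons are mainly qualitative. That stands and sets the severity.

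Four stronger readings are tempting, and the documents do not support them.

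- A reader might infer that the ROC analysis uses a 24-month cut. The 24-month split is in Section 15.7.4 only.
- A reader might infer that the plan treats living patients as deaths. It is silent on the point, and the joint Cox model in Section 15.7.2 does handle censoring.
- A reader might infer immortal-time bias throughout. Section 15.7.2 takes any available tissue. Even in Section 15.7.4 the nominal analysis set is any available tissue, so it is unclear which tests are restricted to paired samples. Within those patients the artefact is conditional, as slope 0 shows.
- A reader might infer that median PFS is biased upward. Only patients alive and progression-free at last contact are affected. PFS follow-up continues after Day 140, and the progression definition in Section 12.6.3 includes clinical decline, which needs no scan.

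**Conclusion.** The point holds, as a minor one. The single-marker and group analyses in Sections 15.7.2 and 15.7.4 do not match the censored endpoint that the plan itself defines, and no handling rule fills the gap. The consequence runs from nothing, with nearly complete follow-up, to a fall in rho from about 0.38 to 0.27–0.34 with 28–44% censored. The time-origin problem is confined to Section 15.7.4 features needing second-surgery tissue, and to features that change with time to surgery. Longer follow-up does not cure it. The PFS wording permits unassessed time to count as progression-free, by an amount that cannot be estimated here. The simulated figures rest on assumed hazard ratios, censoring patterns and surgery timing, and are not predictions for this trial. No dose, safety or accrual rule in the plan depends on these analyses.

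**What to change.** Amend the analysis text as follows.

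- **15.7.4, and single markers in 15.7.2:** replace Spearman correlation with survival by single-marker Cox regression (hazard ratio per SD, with confidence interval) or a concordance measure that accepts censoring. Spearman remains suitable between markers.
- **Short versus long survival:** state the month cut-point for the ROC and use a censoring-aware method for it and for the 24-month contrast. With at most 36 patients, weighted estimates may be unstable, so report intervals. Excluding patients censored before the cut-point, with their number reported, can serve as a sensitivity analysis. It should not be the main analysis, because it keeps early deaths and drops possible long survivors.
- **Features needing post-vaccine tissue:** start the survival clock at the second surgery, or keep the vaccine #1 origin with delayed entry at surgery. State which Section 15.7.4 tests are limited to paired tissue.
- **PFS in 15.6.5:** censor at the last RANO assessment without progression.

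The cost is wording and standard code. No visit, sample or patient number changes. PFS may look slightly shorter.
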